This project is not greater than minimal risk. There is no physical risk to the PCP, study staff, or caregiver participant in the surveys or interviews. The knowledge gained through the interviews and surveys will help assure we are providing NBS and SCT results in ways PCPs and caregivers prefer. The major risk to this study is the discussion of sensitive subject matter. We will conduct interviews virtually via telephone or Teams at a time that is convenient to the participant. In addition, each interview script will be reviewed by the Stakeholder groups to minimize any confrontational or judgmental terminology and assess for face validity and comprehension.

Since the study procedures are not greater than minimal risk, significant adverse events (SAE) are not expected. If any unanticipated problems related to the research involving risks to subjects or others happen during the course of this study (including SAEs) these will be reported to the IRB in accordance with Nemours IRB policies. AEs that are not serious but that are notable and could involve risks to subjects will be summarized in narrative or other format and submitted to the IRB at the time of continuing review.

Potential Benefits of Study Participation

The PCPs within the implementation science pilot trial may receive the following direct benefits: improved knowledge of the importance of NBS and SCT results, enhanced self-efficacy (i.e. confidence) in the disclosure of NBS and SCT results to their patients, improved rates of documentation of NBS and SCT results. If the implementation strategies are found to be acceptable, feasible, and enhance penetration of NBS and SCT result documentation and disclosure they will be further tested within a multi-site implementation trial.

The caregiver participants may not receive any direct benefit to completing the survey. They may receive direct benefit because their PCP is a participant since they may receive additional education from their PCP regarding their child's NBS results. Results from the caregiver participants will help to improve the delivery of care for others in the future.

Payment to Subjects/Families

All compensation will be provided via Greenphire gift card: Name, address, and date of birth will be required to facilitate gift cards.

- Primary Care Provider (PCP) Survey Incentives (1 every 6 weeks during the intervention phase x 4). \$25 per survey. An additional \$25 if all four surveys are completed.
- PCP Qualitative Interviews: \$100 per interview
- Caregiver Participant Survey Incentives: Each caregiver who completes a survey will be entered into a drawing for a \$100 gift card for each survey they complete. There will be 20 lottery gift cards given. Each caregiver that completes the survey will also receive a \$10 gift card.

PUBLICATION

The results of this study may be presented at professional meetings or published in a professional journal. Any personal identifying information will not be included in these presentations or publications.

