Assess the effects of the intervention strategies when delivered “all-in” versus “add-in” by measuring the following outcomes.

- Dispersion: Via EHR extraction- Proportion of children over 2 months of age who have NBS/SCT newly documented (as above).
- Knowledge: Caregiver survey- Proportion of caregivers who accurately reported their child's NBS result.
- Inequities in documentation: Via chart review. Demographic data for each infant: primary care site, sex, race, ethnicity, and insurance type.
- Satisfaction: Caregiver survey.

INVESTIGATIONAL PLAN: Overview

General Schema of Study Design

A two-arm, randomized, interrupted time series design will compare an “all-in” and “add-in” approach. In the “all-in” arm, participants receive all toolkit components at once. In the “add-in” arm, participants will have “multiple interruptions” with sequential addition of components in 6 week increments (**Figure – replace 3 month label with 6 week label**). This will allow for exploration of the added benefit of certain components as compared to the whole toolkit.

Toolkit Components:

- 1) Intervention A: EHR “nudge” within the birth history and/or well-child progress note template
- 2) Intervention B: “lunch-and-learn” sessions (in person or pre-recorded per office preference)
- 3) Intervention C: written educational materials (i.e. post cards, poster, PDF files) to alert PCPs to the importance of SCT documentation and “talking points” to facilitate disclosure;

Duration of Study Participation

Duration of study participation for a site will last a total of approximately 5 months. During the 5 months, PCPs will participate in 4 surveys (15 minutes each) and 1 qualitative interview (30 minutes). Study duration of caregivers will be for survey completion (5-10 minutes).

Total Number of Study Sites/Total Number of Subjects Projected

- 1) Sites: At least 2 sites per arm of the study with at least 10 PCPs in each arm are required.
- 2) PCPs: All PCPs from a given office will be eligible for participation. This will result in at least 20 Nemours PCPs at 4 or more office locations in the Delaware Valley. PCP offices will be purposively chosen to include a wide racial distribution within their patients.
- 3) Caregivers: 500 caregivers of infants with SCT or a normal NBS who are cared for within the specified office location.

Study Population

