Practice level data from the medical record. For each practice location: Patient level demographics (based on having been seen for a well child exam in the 3 years prior to data extraction) will be linked with the primary practice location at the start of the trial. Practice level data will be obtained from a retrospective evaluation of available EHR data and focus on.

- Age and gender distribution
- Race and Ethnicity distribution
- Insurance make-up (Private, Medicaid, other)
- Zipcode to assess median household income of patients seen at that location (census data), Childhood Opportunity Index (COI)
- Number and portion of the patient population with SCT documented in the problem list, medical history section, and diagnosis codes

PCP Consent and Demographic Survey:

Toolkit components will be available to PCPs and office staff in all trial sites regardless of their participation in the research portion of the trial. Use of the toolkit components is as an educational aid and to facilitate routine patient care.

PCPs will initially be approached for consent for the research portion of the trial prior to toolkit initiation. For PCPs who elects to participate in the longitudinal research portion of the trial, a general demographic survey will be completed at time of initial consent. The demographic survey will be facilitated by REDCap and administered electronically. PCPs may enroll at any time during the trial though first attempt at consent will be before toolkit initiation at with each toolkit component rollout and survey point.

“Roll-out” of toolkit components:

- “All-in” arm: The “all-in” trial arm will have access to and be educated regarding the intervention components at one time point via email, via discussion at lunch & learn, via office meeting, or via virtual meeting or recording (depending on site preference).
- “Add-in” arm: Each PCP in the “add-in” arm will receive the intervention components in the same sequence (within a 1 month timeframe of other offices in the “add-in” arm) with 1 component added every 6 weeks.

With each toolkit component rollout an email will be sent to the office staff reminding them about the project, alerting them to the new component, and notifying them about a virtual Teams “office hours” where the study PI will be available for questions or concerns. The study PI will also be available for any virtual or in-person education an office site may request (ie at an office meeting, etc)

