PCP Implementation Surveys: PCPs will receive surveys by email (through REDCap) every 6 weeks. Survey is expected to take 15 minutes to complete. For PCPs in the “all-in” arm, the first survey will be sent prior to the intervention “roll-out” and every 6 weeks after that. For PCPs in the “add-in” arm, the first survey will be sent prior to intervention A “roll-out”, intervention B “roll-out”, intervention C “roll-out”, and then 6 weeks after. The survey is created specifically for this study and focused on the acceptability of using the intervention component, feasibility of using the intervention component, the opportunity costs of using the intervention component (the time it takes to use the intervention, the perceived effect on other discussion topics with well child visits), and the intention and confidence (i.e. self-efficacy) to document and discuss NBS and SCT results.

PCP Qualitative Interviews: At completion of the Intervention period, PCP participants will be contacted to schedule the qualitative interview. Interviews will be expected to last ~30 minutes. Interviews will be completed over the telephone or using a video conferencing platform. If video conferencing is used, participants will be instructed to keep their camera turned off, so their image will not be recorded. The participant will be notified verbally when the recording has started and when it has stopped.

The qualitative interviews will assess their experience with the components and intention to document and disclose NBS/SCT results in the future.

Infant Identification:

Infants seen at a participating site during the retrospective and intervention period for a well child visit before 2 months of age will be identified through EHR data extraction on a rolling basis (i.e. once a month during the trial) based on ICD10 code for a new patient/well child exam (ICD 10: Z00.110, Z00.111, Z00.121, Z00.129, Z00.00, Z00.01 or CPT: 99381, 99382, 99383, 99384, 99385, 99391, 99392, 99393, 99394, 99395).

Documentation and Discussion of NBS/SCT results for all infants identified: via chart review. For each infant identified, the following data will be collected via EHR extraction and manual chart review:

- Email
- Preferred language
- MRN (to facilitate manual chart review)
- Gender
- Race, ethnicity
- Insurance
- Zipcode (to assess Childhood Opportunity Index)
- Phase of study they were first seen for a WCC (retrospective, “all-in” A/B/C, Intervention A, Intervention B, Intervention C)

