- **PCP Recruitment.** An introductory email (through REDCap) will be sent to all staff identified by the PIC/office manager for any site participating in the trial explaining the study before the Intervention period. The PI will be available to attend any office meetings or question and answer sessions that the PIC or PCPs request. PCPs will be informed that participation in the research components is voluntary, will not affect their employment, and that they will receive access to the toolkit components without participation. The study coordinator and/or PI will follow-up with PCPs by telephone, email, virtual meeting, or in person to answer additional questions.

They will be given the contact information for the PI and study coordinator for any questions or withdrawal from participation. Three follow-up requests will be sent to non-responders at ~1 week intervals and then at 6 week intervals (ie when interventions are rolled out and surveys distributed) during study time period.

- **PCP Retention.** Trial procedures will include every 6 week on-line REDCap facilitated surveys and a final qualitative interview. Surveys will include an introductory expression of appreciation for their continued participation and reminder of reason for the trial. Incentive compensation will be given after each study procedure (survey or qualitative interview) is completed. Three reminder e-mails and/or telephone calls will be provided for each survey. For surveys, we will also include the option of completing the survey by phone or on paper if the participant prefers. We will provide flexibility in timing for the final qualitative interview to accommodate their work schedule and maximize participation. PCPs will be compensated \$25 per survey they complete and \$100 for the qualitative interview. PCPs will receive an additional \$25 if all four surveys are completed.
- **Caregiver Survey Recruitment:** Infants seen at a participating site for a well child visit before 2 months of age will be identified through EHR data extraction on a rolling basis

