- Feasibility: Percent of PCPs who use individual toolkit components.
- Adoption/Self-efficacy: PCP survey. Intention and confidence to document/discuss NBS/SCT result.
- Cost: PCP survey: Perceived time (in mins) to document and discuss NBS/SCT result, effect on other discussion topics during the visits.
- Dispersion: Via EHR extraction- Proportion of children over 2 months of age who have NBS/SCT newly documented (as above).
- Knowledge: Caregiver survey- Proportion of caregivers who accurately reported their child's NBS result.
- Inequities in documentation: Via chart review. Demographic data for each infant: primary care site, sex, race, ethnicity, and insurance type.
- Satisfaction: Caregiver survey.

Statistical Methods

Unit of analysis will be the individual PCP (i.e. pre/post) and by trial arm with the primary end point being the rate of documentation and disclosure of NBS and SCT (penetration).

Data will be summarized in numeric and graphic forms. Mean and standard deviation or median and interquartile range will be used for summarizing numerical variables and frequencies and percentages will be used for categorical variables. PCP's EHR documentation and disclosure of newborn screen (NBS) and sickle cell trait (SCT) carrier results will be presented by pre-post intervention as well as by intervention groups. The primary end point of the study is to compare the proportion of PCP's/ EHR documentation and disclosure of NBS and SCT between pre- and post- intervention periods.

Generalized linear mixed effects model will be used for the analysis of the primary end-point. Odds ratio with confidence interval will be provided for the documentation and disclosure. Generalized linear mixed effects model will also be used to compare the proportion of post-intervention documentation and disclosure over time (monthly) between two intervention groups. Mean score of acceptability for each intervention (A, B, C) as well as mean total score for all three interventions will be compared between two intervention groups. Similarly, other survey results such as Self-Efficacy of PCP to document NBS and time cost will be compared between two intervention groups. Also, dispersion, caregiver knowledge and caregiver satisfaction will be

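### PCPs can join the survey study after their office has received toolkit components that differ by arm, and the arm comparisons of acceptability, self-efficacy and time cost have no rule for these late joiners

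*Combined protocol and SAP*

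**What the plan says.** All references are to the combined protocol and SAP.

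- **Exposure does not depend on consent.** The section PCP Consent and Demographic Survey states: "Toolkit components will be available to PCPs and office staff in all trial sites regardless of their participation in the research portion".
- **Enrolment stays open.** Same section: "PCPs may enroll at any time during the trial though first attempt at consent will be before toolkit initiation". Under Recruitment of Participants, PCP Recruitment: "Three follow-up requests will be sent to non-responders at ~1 week intervals and then at 6 week intervals". The six-week invitations are tied to component roll-outs and survey mailings, so entry after exposure is actively sought.
- **Only the first survey precedes the toolkit.** PCP Implementation Surveys, all-in arm: "the first survey will be sent prior to the intervention" is rolled out. Add-in arm: "the first survey will be sent prior to intervention A", with later surveys before B, before C, and six weeks after that.
- **Planned comparison.** Statistical Methods: "Mean score of acceptability for each intervention (A, B, C) as well as mean total score for all three interventions will be compared" between the two groups, with self-efficacy and time cost handled similarly. Tests are chosen as appropriate from a list that includes ANCOVA and linear mixed models. No baseline covariate is named, no PCP-survey analysis set is defined, and nothing is said about late joiners or a missing first survey.
- **Status of the outcomes.** Acceptability, self-efficacy and cost appear under Primary Objectives, but under Secondary Endpoint in Statistical Considerations, where penetration is the primary endpoint.

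**The concern.** Offices are randomised, but survey respondents are PCPs who choose whether and when to join. A PCP who consents before roll-out does so without experience of the toolkit. A PCP who consents at a later invitation has had the chance to form a view of it, and that view may influence the decision to join. Because the two arms have received different components when the same invitation goes out, this selection can act differently by arm. An arm difference in mean scores may then partly reflect who chose to respond.

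Self-efficacy and time cost have a second problem. Both can be measured before the toolkit arrives, and adjusting for that value would protect the comparison, but a late joiner does not have it.

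The protocol says the pilot's main goal is a reliable estimate of effect size, and Sample Size Justification extends this to the survey results. A biased arm contrast would pass into the planning of the next trial.

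**Working it through.** The plan gives no SD, effect size, power or late-enrolment rate for the PCP survey outcomes, so there is no figure of its own to reproduce. The check has three steps.

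**1. What an office has received at each invitation.** Count weeks from first roll-out, with one add-in component every 6 weeks and four surveys 6 weeks apart:

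| Survey / invitation | All-in | Add-in | Pre-toolkit survey possible? |
|---|---|---|---|
| Before first roll-out | none | none | yes |
| Week 6 | A+B+C | A | no |
| Week 12 | A+B+C | A+B | no |
| Week 18 | A+B+C for 18 weeks | A+B+C, with C for 6 weeks | no |

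The add-in column takes the invitation as going out with the survey that precedes the next component. An invitation sent with the roll-out itself would add that component, newly announced. Content or length of exposure still differs by arm.

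**2. Size of a spurious arm difference.** Let f be the share of an arm's respondents who joined late and g the late-minus-early score gap in SD units. With no true effect, an arm's mean is shifted by f × g, so

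spurious difference = f(all-in) × g(all-in) − f(add-in) × g(add-in).

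With a common gap this is [f(all-in) − f(add-in)] × g. The plan supplies 10 PCPs per arm and a two-sided 0.05 level; f and g are assumptions. At 10 per arm the standard error of the difference is √(1/10 + 1/10) = 0.447 SD. The rejection rate comes from a noncentral t with 18 degrees of freedom and noncentrality bias / 0.447, ignoring clustering by office and the slight extra spread from mixing early and late joiners.

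| Late share, all-in vs add-in | g = 0.5 SD | g = 1.0 SD | False-positive rate (nominal 5%) |
|---|---|---|---|
| 20% vs 20% | 0 | 0 | 5% |
| 30% vs 10% | 0.2 × 0.5 = 0.10 SD | 0.2 × 1.0 = 0.20 SD | 5.5% to 7.1% |
| 50% vs 10% | 0.4 × 0.5 = 0.20 SD | 0.4 × 1.0 = 0.40 SD | 7.1% to 13.5% |
| 50% vs 0% | 0.5 × 0.5 = 0.25 SD | 0.5 × 1.0 = 0.50 SD | 8.3% to 18.5% |

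The sign reverses if the add-in arm has more late joiners or if late joiners score lower. The documents do not settle the direction.

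**3. Precision if only pre-roll-out PCPs are analysed.** Difference detectable with 80% power, two-sample t-test, clustering ignored: 1.33 SD at 10 per arm, 1.51 at 8, 1.63 at 7 and 2.02 at 5.

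**The case against.** The strongest reply is that these are secondary endpoints of a pilot, that every input to the bias calculation is assumed, and that equal late shares with equal selection give no bias. A bias of 0.1 to 0.2 SD is small beside a detectable difference of 1.33 SD. Late enrolment may also help reach the required 10 PCPs per arm. PCPs who volunteer early are themselves selected and may represent an office less well. ANCOVA and mixed models are already listed, and consent is taken electronically in REDCap, so late joiners should be identifiable.

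Much of this stands. It limits the size of the point and argues against making early joiners the only main analysis set. It does not supply the missing rule: no survey-1 covariate is named and no analysis distinguishes late joiners. The pilot label does not help either, since an effect estimate for planning is what the pilot is meant to deliver.

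A reader might infer more than the documents support:

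- **That late joiners have already used the toolkit.** The components are available to them. Use is itself an outcome (feasibility), so exposure is shown and use is not.
- **That the plan specifies a pre/post survey analysis which late entry breaks.** "Unit of analysis will be the individual PCP (i.e. pre/post) and by trial arm" might suggest this, but the sentence goes on to name penetration, the EHR endpoint. For the surveys, only between-arm comparisons are stated.
- **That every survey outcome lacks a needed baseline.** Acceptability of a component has no true value before the component is met, and an add-in PCP who joins before B or C still has a survey before those components. The missing pre-toolkit value matters for self-efficacy and time cost.
- **That the primary endpoint is biased by late consent.** Chart data are collected for all infants identified at participating sites, so penetration is not directly affected.

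**Conclusion.** The point holds for the arm comparisons of acceptability, self-efficacy and time cost. The plan permits and invites PCPs to enter after randomisation and exposure, that exposure differs by arm, and the stated analysis does not separate late entrants. Self-efficacy and time cost also lose the available baseline adjustment for these PCPs.

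The size cannot be known from the documents. It runs from zero, when late shares and selection match across arms, to 0.1 to 0.2 SD with late shares of 30% and 10% and a gap of 0.5 to 1.0 SD. Reaching 0.5 SD needs half of one arm and none of the other to join late, with a 1 SD gap. This is a gap in the analysis plan worth closing before the survey data are analysed, and not a flaw in the primary endpoint.

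**What to change.** Enrolment can stay as it is. In Statistical Methods:

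1. Adjust the arm comparisons of self-efficacy and time cost for the survey-1 value, by ANCOVA or a linear mixed model, both already listed. For time cost, use the minutes to document and discuss results, which can be asked before roll-out. Acceptability needs no such adjustment.
2. Classify each PCP as consenting before or after their office's first roll-out, and report the number, timing and scores of late joiners by arm.
3. Prespecify each PCP-survey arm comparison in two sets: PCPs who consented and completed survey 1 before roll-out, and all PCPs. State how the all-PCP analysis treats a missing survey 1, for example a mixed model with survey 1 as one of the repeated outcomes. Draw an arm conclusion only where the two analyses agree, and define agreement in advance by direction and rough size, since significance in both is too much to ask of about 10 PCPs per arm.

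The cost is wording and one extra analysis per outcome. The downside is lower precision in the pre-roll-out set: with 7 PCPs per arm the detectable difference is about 1.6 SD against 1.3 SD with 10, before clustering. That set also remains one of early volunteers, which is a reason to show both analyses.

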Participants will be Nemours primary care offices, Nemours PCPs, and caregivers of children seen for infant primary care well visits at the enrolled office.

Inclusion Criteria:

- Sites: Nemours primary care locations within the Delaware Valley that provide well child care to infants
- PCPs: All Nemours PCPs (physicians and nurse practitioners) at included office locations.
- Caregivers: English speaking caregiver of an infant seen at a participating office location for a well visit before 2 months of age (2 months = 60 days) with an email address available within the EHR.

Exclusion Criteria:

- Caregivers and PCPs: Unable to converse in English.
- Caregivers: Caregivers of infant seen for a first well visit at 61 days of age or older

Subjects that do not meet all of the enrollment criteria may not be enrolled. Any violations of these criteria must be reported in accordance with IRB Policies and Procedures.

STUDY PROCEDURES

Site selection: Emails will be sent to the physician-in-charge of Nemours outpatient office locations within the Delaware Valley with a description of the study and an invitation to participate. For those interested in participating as a site, a REDCap interest survey will be included asking for site specific information (i.e. location, name/contact information of physician-in-charge (PIC), name/contact information of office manager or other person designated by the PIC to handle communication about the trial, Number of PCPs at site). Sites will be matched and paired to create dyads/triads of locations with similar racial demographics of patients (i.e. a dyad with the majority of patients documented as Black or Hispanic, etc). For sites selected for participation in the trial, name/contact information will be collected from the PIC or office manager for all PCPs at the office and anyone else they would like to receive communication about the trial (i.e. nursing staff). An introductory email will be sent to all staff identified by the PIC/office manager explaining the study.

Randomization: Sites will then be randomized within each dyad (i.e. one clinic randomized to the “all-in” arm and the other to the “add-in” arm). All PCPs from the same location will be assigned to the same trial arm.

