- Presence/absence of NBS
- Result of hemoglobinopathy NBS
- Presence/absence of NBS result documented in 1) problem list, 2) medical history, 3) progress notes
- Presence/absence of a disclosure conversation about NBS result in progress notes (including topics discussed: inheritance patterns, medical implications, reproductive implications, hematology/genetics consultation)
- Presence/absence of NBS results in After Visit Summary communication

Caregiver Survey from retrospective period:

Caregivers of three groups of infants will be surveyed if they are identified as speaking English (through EHR demographic data) and with an email address in the EHR:

- Group 1: All infants with SCT seen before 2 months of age within the 6 month retrospective period
- Group 2: All infants identified as Black or Hispanic seen before 2 months of age within the 6 month retrospective period

- Group 3: Infants seen before 2 months of age within the 3 month retrospective period and not included in group 1 or 2

Caregiver Survey during Intervention Period:

Caregivers from the participating office locations of three groups of infants will be surveyed if they are identified as speaking English (through EHR demographic data) and with an email address in the EHR:

- Group 1: All infants with SCT
- Group 2: All infants identified as Black or Hispanic
- Group 3: Infants seen in the first half of the month and not included in group 1 or 2

Caregivers will receive a survey at 2 and 6 months of age (+/- 1 month) delivered by email (through REDCap). Survey is expected to take less than 10 minutes to complete. Consent and survey responses will be obtained electronically. The survey will inquire about results of the NBS, preferences for information receipt, and satisfaction with well child visit.

Recruitment of Participants

- **See site selection under Study Procedures**

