We are requesting to waive a signature for consent, as the participants will be asked to document consent/assent via REDCap survey, and reaffirm consent/assent verbally prior to the qualitative interview. The surveys and qualitative interview presents no more than minimal risk to the participants. Additionally, we are not asking for any additional personal health information or identifiers apart from Greenphire information. The consent document would be the only other document connecting the survey responses and the PCP. The participants will be provided with an information sheet in recruitment emails and prior to starting the REDCap survey.

We are asking for a waiver of HIPAA authorization. The survey study involves no more than minimal risk to the participant. Additionally, the HIPAA form would be the only other document connecting survey response and the participant. Because we want the participants to be as honest as possible, we do not want the participant to feel that we can connect them to their responses and that connection could include the HIPAA documentation.

PHI will be used 1) to ensure eligibility of participants; 2) to contact for recruitment; and 3) to appropriately describe our sample. We will collect identifiable information (i.e. DOB and address) for those who receive a gift card to process study payment through Greenphire. This data will not be provided to or used for anything aside from payment. As this study will be conducted entirely remotely, it cannot be conducted without access to and use of PHI such as

Subject Completion/Withdrawal

contact information.

Subjects may withdraw from the study at any time without prejudice to their care or employment. The PI may withdraw a participant from the study if it is learned that they did not fulfill eligibility criteria. It will be documented whether or not each subject completes the study.

STATISTICAL CONSIDERATIONS

Evaluation of the Toolkit will focus on Proctor's framework of IS outcomes:⁴⁷

Primary Endpoint

- Penetration (via interrupted time series): via EHR extraction. Rate of scanned NBS results available in the EHR. Rate of documentation and disclosure of NBS and SCT result at < 2 months of age in each of the following: the problem list, the medical history section, and progress note. Evaluate monthly: retrospectively (pre intervention) and prospectively (post intervention).

Secondary Endpoint

- Acceptability: via PCP survey for each toolkit component.

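### Infants are labelled by phase at first well visit but scored up to 2 months of age, so late pre-period infants straddle the first roll-out, with no transition rule or chart-reading age stated

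*Combined protocol and SAP*

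**What the plan says.** - **Phase label.** Under Documentation and Discussion of NBS/SCT results (Study Procedures), the only infant-level exposure item is "Phase of study they were first seen for a WCC". The categories are retrospective, all-in, and interventions A, B and C.
- **Endpoint.** The Primary Endpoint section gives "Rate of documentation and disclosure of NBS and SCT result at < 2 months of age in each of the following" of three chart locations. The caregiver inclusion criterion turns this age into days: "well visit before 2 months of age (2 months = 60 days". The Sample Size Justification uses a different limit, under 1 month.
- **Roll-out.** The add-in arm proceeds "with 1 component added every 6 weeks", and an add-in office's dates fall "within a 1 month timeframe of other offices" in that arm.
- **Chart data.** Infants are identified "on a rolling basis (i.e. once a month during the trial". The outcome item is "Presence/absence of NBS result documented in 1) problem list, 2) medical history, 3) progress notes". Neither a date nor an age at reading is listed, although the list may not be exhaustive. Caregiver Survey Recruitment describes a first extraction at the start of the intervention phase, then monthly ones.
- **Analysis.** Statistical Methods specifies a pre/post mixed model and a monthly post-period comparison between arms. It names no transition group, lag, washout or time-varying exposure.
- **Pre-period length.** The caregiver survey section refers to infants seen "within the 6 month retrospective period". The chart review itself has no stated length.

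**The concern.** A label fixed at the first visit and an outcome read up to 60 days of age cover different stretches of time. An infant first seen a few weeks before roll-out counts as unexposed, yet may be documented because of the toolkit. If the chart is instead closed at roll-out, that infant has had less time to be documented than the others. Either way the pre-period rate is not a clean pre-intervention rate. This matters because the plan calls a reliable effect size the pilot's main goal, and a larger sample does not remove the bias. In the add-in arm the same mismatch recurs at each new component, which affects the exploration of single components promised under General Schema of Study Design.

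**Working it through.** **Inputs from the documents.** Window 60 days. Add-in phase 6 weeks = 42 days. Documentation target 20% to 50%. Planned minimum 1080 infants per period, 540 per arm. The last figure reproduces: 20 PCPs x 6 infants per month x 9 months = 1080, and half is 540.

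**Pre-period length L.** 6 months = 182.6 days (caregiver survey section), or 9 months = 273.9 days (what 1080 infants need at 6 per PCP per month).

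**Assumptions (not in the documents).** First visit at day 5, even arrivals, a pre-period that runs up to roll-out, additive effects, and 10 points for each of A, B and C. Documentation timing is either spread evenly from day 5 to day 60, or front-loaded (50/30/20% at days 5/14/30).

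**1. Share of pre-period infants crossing the first roll-out.** The remaining window is 60 - 5 = 55 days. 55/182.6 = 30%; 55/273.9 = 20%. A first visit anywhere from day 3 to day 28 gives 31% to 18%, or 21% to 12%.

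**2. Share of pre-period documentation falling after roll-out.** Even: half the crossing share, 27.5/L. Front-loaded: (0.3 x 9 + 0.2 x 25)/L = 7.7/L.

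**3. Late reading (after the window closes).** The pre-period rate rises by the share times the effect in force. All-in uses 30 points. Add-in uses 10 points for A. In the even case add-in also gains about 0.1 point from B, since 55 - 42 = 13 days can fall after the second roll-out. Pooled is the mean of the two arms.

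| | Even, 6 mo | Even, 9 mo | Front-loaded, 6 mo | Front-loaded, 9 mo |
|---|---|---|---|---|
| Share after roll-out | 0.151 | 0.100 | 0.042 | 0.028 |
| All-in dilution (points) | 4.5 | 3.0 | 1.3 | 0.8 |
| Add-in rise (points) | 1.6 | 1.1 | 0.4 | 0.3 |
| Pooled dilution (points) | 3.05 | 2.04 | 0.84 | 0.56 |

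If all documentation occurs at the first visit, every entry is zero.

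**4. Early reading (on the day of roll-out).** The same share of documentation is lost from the 20% baseline: 20 x 0.151 = 3.0, 20 x 0.100 = 2.0, 20 x 0.042 = 0.8 and 20 x 0.028 = 0.6 points. The pre-period rate is too low by these amounts. The effect is inflated by them, provided post-period infants are followed to the end of their window.

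**5. Benchmark.** Unclustered standard error of the pre/post difference: per arm sqrt((0.16 + 0.25)/540) = 2.8 points; pooled sqrt(0.41/1080) = 1.95 points.

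**6. Add-in phases.** 60 - 42 = 18, so every phase A or B infant first seen by day 18 reaches the next component before the window closes. The mean share of a phase B infant's documentation that falls under C is 1 - 21/55 = 0.62 (even) or 7.7/42 = 0.18 (front-loaded). Phase C minus phase B then shows only 0.38 or 0.82 of C's true effect.

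**7. Under the 1-month limit (taken as 30 days).** 25/182.6 = 14% or 25/273.9 = 9% of pre-period infants cross, as do 25/42 = 60% of phase A and B infants. The window no longer outlasts a phase, but the overlap remains.

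**The case against.** **Direction.** A reader might infer that exposed time certainly enters the pre-period and dilutes the effect. The documents do not support that. They do not say when charts are read, and the extraction timing given for caregiver recruitment would lead to truncation and the opposite bias. If post-period charts were also read at their monthly pull, they too would be truncated and the net direction would be open. This stands: the direction is conditional.

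**Comparison between arms.** A reader might also infer that the early gap between the arms in the monthly comparison is understated, because add-in infants go on to receive later components. That does not follow. The arms are two delivery strategies, and receiving B or C on schedule is part of the add-in strategy. The gap between infants entering in the same month is a valid contrast of those strategies.

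**Component effects.** The plan promises only exploration of components and specifies no by-phase test, so this part concerns how such a result would be read, not a planned analysis.

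**Size.** Visit age, documentation timing and component effects are all assumed. The front-loaded dilution is below one standard error, and the lower limit is zero. This stands too.

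What the objections do not remove is the mismatch between label and window. No choice of reading time gives late pre-period infants a full 60-day window free of the toolkit.

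**Conclusion.** The point holds for the pre/post contrast. Infants first seen within about 60 days of a site's first roll-out are labelled retrospective without a complete unexposed window, and the plan has no rule for them. On the stated assumptions they make up about 30% or 20% of the pre-period. With late reading the pooled 20% to 50% contrast is diluted by about 2.0 to 3.1 points (even timing) or 0.6 to 0.8 (front-loaded). For all-in alone the figures are 3.0 to 4.5 and 0.8 to 1.3, against an unclustered standard error of about 2.8 points at 540 per period. With reading at roll-out the bias has the opposite sign. The monthly comparison between arms is not biased by this. A by-phase reading of the add-in arm that uses the first-visit label would understate C if C has any effect. Confidence is high in the overlap and low to moderate in its size. This is a worthwhile, cheap improvement and not a fatal flaw.

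**What to change.** 1. Record date of birth, well-visit dates, documentation and scan dates, and each site's roll-out dates. Score every infant's outcome by the same age from dated entries.
2. For the pre/post contrast, place infants whose window crosses their own site's first roll-out in a transition group outside the pre-period. Start the retrospective pull about 55 to 60 days earlier to replace them.
3. Report any add-in by-phase result as exploratory and as an entry-cohort effect that includes later components. Alternatively, attribute each documentation event to the components live on its date.
4. Reconcile the under-1-month limit in the Sample Size Justification with the under-2-month limit in the Primary Endpoint section.

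**Cost.** Dates must be abstracted for the outcome items, and about 2 more months of retrospective charts are needed. At 20 PCPs and 6 to 10 infants per PCP per month, 55 days is (55/30.44) x 120 to 200 = about 217 to 361 charts.

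Exclusion without the longer pull would be costly. At 6 infants per PCP per month, a 6-month pre-period falls from 720 to 503 infants (at 2.1%, 15 to 11 with SCT). A 9-month one falls from 1080 to 863 (23 to 18 with SCT, against the 21 the plan requires). The longer pull replaces the excluded infants only; it does not by itself bring a 6-month pre-period at that volume up to 1080.
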